- **d.** Consent. Will you obtain consent now from subjects for the banking and/or future sharing?

Yes → If yes, be sure to include the information about this consent process in the consent form (if there is one) and in your answers to the consent questions in Section 6.

e. Withdrawal. Will subjects be able to withdraw their data/specimens from banking or sharing?

→ If yes, describe how, and whether there are any limitations on withdrawal.

Example: data can be withdrawn from the repository but cannot be retrieved after they are released.

f. Agreements for sharing or release. Confirm by checking the box that you will comply with UW (and, if applicable, UW Medicine) policies that require a formal agreement between you and the recipient for release of data or specimens to individuals or entities other than federal databases.

Data Use Agreements or Gatekeeping forms are used for data; Material Transfer Agreements are used for specimens (or specimens plus data. Do not attach your template agreement forms; the IRB neither reviews nor approves them

x Confirmed

5.9 Communication with subjects during the study. Describe the types of communication (if any) you will have with already-enrolled subjects during the study. Provide a description instead of the actual materials themselves.

Examples: email, texts, phone, or letter reminders about appointments or about returning study materials such as a questionnaire; requests to confirm contact information.

If technical issues are identified or if participants have gone 'dark' (missing data over a period of time) we will provide a text message or call checking in with the participant. Based on their response (i.e. express needing technical support, or non-response), an RA will contact the participant to ensure their phone is working and to assess if they are still interested in participating. If a participant has gone dark for in extended period of time and are unable to be reached by phone, a letter will be sent to their mailing address (email or physical mailing address: copy of letter attached). PHI will not be transmitted in text messages or emails.

5.10 Future contact with subjects. Do you plan to retain contact information for your subjects so that they can be contacted in the future?

No x Yes

→ If yes, describe the purpose of the future contact, and whether use of the contact information will be limited to your team; if not, describe who else could be provided with the contact information. Describe your criteria for approving requests for the information.

Examples: inform subjects about other studies; ask subjects for additional information or medical record access that is not currently part of the study proposed in this application; obtain another sample.

Future contact would be limited to our research team and would be for the purpose of recruitment in new studies our team would be conducting.

5.11 Alternatives to participation. Are there any alternative procedures or treatments that might be advantageous to the subjects?

If there are no alternative procedures or treatments, select "No". Examples of advantageous alternatives: earning extra class credit in some time-equivalent way other than research participation; obtaining supportive care or a standard clinical treatment from a health care provider instead of participating in research with an experimental drug.

Pai	CICIP
Х	No
	Ye
	S

→ If yes, describe the alternatives.

- **5.12 Upload to the Supporting Documents** SmartForm of **Zipline** all data collection forms that will be directly used by or with the subjects, and any scripts/talking points you will use to collect the data. Do not include data collection forms that will be used to abstract data from other sources (such as medical or academic records, or video recordings.
 - **Examples**: survey, questionnaires, subject logs or diaries, focus group questions.
 - **Translations must be included**. However, you may wait to provide them until you know that the IRB will approve the English versions, especially if the translations will cost money.
 - For materials that cannot be uploaded: upload screenshots or written descriptions that are
 sufficient to enable the IRB to understand the types of data that will be collected and the nature of
 the experience for the participant. You may also provide URLs (website addresses) or written
 descriptions below. Examples of materials that usually cannot be uploaded: mobile apps; computeradministered test; licensed and restricted standardized tests.
 - For data that will be gathered in an evolving way: This refers to data collection/questions that are not pre-determined but rather are shaped during interactions with participants in response to observations and responses made during those interactions. If this applies to your research, provide a description of the process by which you will establish the data collection/questions as you interact with subjects, how you will document your data collection/questions, the topics you plan to address, the most sensitive type of information you will plan to gather, and the limitations (if any) on topics you will raise or pursue.

Use this text box (if desired) to provide short written descriptions of materials that cannot be uploaded, such as URLs, and/or a description of the process you will use for data that will be gathered in an evolving way.

5.13 Send HSD a Confidentiality Agreement if you will obtain or use any private identifiable UW records without subject consent (for example, screening medical records or class grades to identify possible subjects).

The Confidentiality Agreement form must be completed, printed, signed, and mailed to the Human Subjects Division at Box 359470. Your IRB application cannot be approved until we receive the Confidentiality Agreement.

6 CHILDREN (MINORS) and PARENTAL PERMISSION

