Aim 1. Evaluate and compare implementation outcomes. We will measure and compare FOCUS penetration among providers, acceptability within agencies, cost and cost effectiveness associated with FOCUS within CMHCs using EF or IF implementation approaches.

Aim 2. Examine moderators and mediators of implementation effects. We will examine the extent to which CMHC characteristics (i.e., readiness for change, organizational culture, urban vs. rural setting) moderate implementation outcomes. Consistent with the NIMH experimental therapeutics approach, we will evaluate mechanisms of action and examine whether absorptive capacity (practitioner—level target) mediates the effect of EF and IF on implementation outcomes.

Aim 3. Evaluate and compare patient outcomes. We will measure and compare whether the

implementation strategies differentially affect FOCUS patients' psychiatric symptom severity, recovery, and illness management capacity. We will also examine whether mHealth engagement (patient-level target) mediates the effects of EF and IF on patient outcomes.

1.6 Study design. Provide a one-sentence description of the general study design and/or type of methodology.

Your answer will help HSD in assigning applications to reviewers and in managing workload. Examples: a longitudinal observational study; a double-blind, placebo-controlled randomized study; ethnographic interviews; web scraping from a convenience sample of blogs; medical record review; coordinating center for a multi-site study.

multi-site site hybrid type III effectiveness/implementation study

1.7 Intent. Check all the descriptors that apply to your activity. You must place an "X" in at least one box.

This question is essential for ensuring that your application is correctly reviewed. Please read each option carefully.

Desci	riptor
1.	. Class project or other activity whose purpose is to provide an educational experience for the researcher (for example, to learn about the process or methods of doing research).
2.	Part of an institution, organization, or program's own internal operational monitoring.
3.	s. Improve the quality of service provided by a specific institution, organization, or program.

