
return on investment considerations that would make the addition of an internal facilitator more appealing and contextually appropriate. There may be benefits in using recognized members of the clinical setting who can capitalize on existing relationships and awareness of workflows and practice processes, have legitimacy and trust, have access to patient records, engage in clinical team meetings, and conduct facilitation activities with CMHC staff in person, thus enhancing penetration. We propose to use IF and EF to engage providers and compare the effects of both models on patient and implementation outcomes. Key implementation variables. A host of implementation research outcomes have been articulated for studies focused on improving the quality of health services. 46 The promise of mHealth rests largely in its ability to efficiently transform contemporary healthcare at a large scale. 47, 48 Therefore, examining the impact of the implementation strategy on penetration of a practice within a service setting, acceptability (perception that an innovation is agreeable, palatable, or satisfactory), cost-effectiveness (value for money of alternative approaches) and affordability (i.e., the expense of the particular intervention) are particularly critical. Organizational factors are critical to effective implementation: With growing recognition that "bad systems trump good programs," 49 the role of organizational influences on implementation has become widely recognized. 50-52 Critical factors influencing implementation success include the extent to which an organization is ready to engage in a change effort. 53 Organizational readiness for change varies depending on how much members of an organization determine task demands, resource availability, and situational factors to be favorable. A strong organizational culture (i.e., shared assumptions, values, and beliefs that govern how people behave in an organization) has repeatedly been found to predict positive implementation and service quality outcomes.52, 54, 55 We will directly examine whether our implementation strategies have a differential impact on implementation outcomes depending on an organization's culture and readiness for change.

b. Experience and preliminary work. Briefly describe experience or preliminary work or data (if any) that you or your team have that supports the feasibility and/or safety of this study.

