4.1 Procedures. Describe how you will identify, recruit, and screen subjects. Include information about: how, when, where, and in what setting. Identify who (by position or role, not name) will approach and recruit subjects, and who will screen them for eligibility.

Mental health providers will describe the study to their patients to gauge interest-clinicians will obtain interest and will pass along contact information to the research team from interested patients or will provide the study URL (hosted by Qualtrics) for patient's to enter their contact, express interest and assess eligibility.

Patient Participants will be identified based on a protocol previously used by the Washington State CMHC implementation effort.

The protocol entails coordinating with middle managers and IT staff at each agency to audit Electronic Health Records (EHRs) by diagnosis. This procedure generates a list of active patients who meet diagnostic inclusion criteria. "Active status" is defined by the research team as seen in the CMHC for services within the several months. For agencies that lack the capability to execute a search by diagnosis among active patients, caseload audits are delegated to the treatment teams.

Once the "active status" list has been generated, it will then be given to care coordinators or treatment team leaders along with a script to introduce the study to eligible individuals, provide a brief verbal introduction to the study along with a 1-page handout prepared by the research team.

Patients can indicate their interest through accessing a secure study webpage (hosted by Qualtrics) or by giving permission to their clinician to pass along their contact information to the research team. On the study webpage they will be asked for their first and last name, phone number, the clinic they currently receive care from and to answer 3 inclusion questions + interest in future studies; 1. If they have a smartphone with data plan that can support the FOCUS app, 2. If they have ever used FOCUS before, and 3. If they plan to leave treatment in the next 6 months. 4. If they are interested in being informed about future research studies.

Consent forms will be available to potential participants in one of three ways; 1. They can pick up a printed form at the participating clinic, and/or 2. A copy can be downloaded from the study webpage, and/or 3. Emailed/texted to the potential participant before research staff reach out via phone.

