- A list of active participants will be generated either through culling EMR data or talking with clinical teams that will serve as the primary list for their clinical teams to approach to describe the study and gauge interest.
- Services billed- no identifiers will be shared with the research team

Mental Health Provider Participants:

Select mental health providers will be invited to complete an online assessment with the research team. Staff participants will be invited to complete a confidential online survey. This includes exposure to the FOCUS app, if strategies or the program was incorporated into their treatment plans, and perceptions of how the program was adopted and implemented at their clinic.

Mental Health Provider Assessment:

Providers who receive FOCUS data

- Offered mHealth, i.e., the percent of each practitioner's eligible patients who are offered FOCUS
- Treatment Initiation, i.e., percent of consenting patients who followed their practitioner's guidance and went on to download FOCUS onto their smartphone and interact with the system at least once. Dashboard Use, i.e., the average number of times each practitioner logs on to the online FOCUS dashboard to view their individual patients' uploaded FOCUS data

The following will be captured via online confidential** survey (Qualtrics):

- The perception among practitioners that an innovation is agreeable, palatable, or satisfactory. (Measured via AIM / IAM / FIM).
- ORIC: Organizational Readiness for Implementing Change

Providers at the clinic who may not have been directly involved with the FOCUS Intervention (to provide contextual factors) through online confidential survey (Qualtrics):

- Organizational Readiness to Change Assessment (ORCA)
 - CMHC staff participants will complete 23 items using a 5-point bipolar rating scale (1-Strongly agree to 5-Strongly disagree). Constructs evaluated include clinical cooperation within the practice, clarity in patient care goals and process, level of support (e.g., training, budget, staffing) and typical receptivity to guidance (staff) and feedback (leadership).
- Absorptive capacity will be measured among CMHC practitioners who were engaged in IF or EF implementation at 0, 3, and 6 months using the 14-item ACAP Scale.
 - o The ACAP Scale evaluates dimensions of absorptive capacity including
 - Acquiring (e.g., searching for new information, motivation to use information)

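### The only provider uptake measures are listed for providers who receive FOCUS data, and nothing provides for counting clinicians with eligible patients who never offer it, so the Aim 1 penetration comparison can be biased

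*Protocol*

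**What the plan says.** Aim 1 (protocol section 1.5) states: "We will measure and compare FOCUS penetration among providers". The background (section 1.8a) describes the outcome as "penetration of a practice within a service setting", which makes the clinic the reference.

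Section 5.1, Mental Health Provider Assessment, sorts provider measures under two labels.

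- Under "Providers who receive FOCUS data" stand the three uptake measures. The first is "Offered mHealth, i.e., the percent of each practitioner's eligible patients who are offered FOCUS". The second, Treatment Initiation, is the "percent of consenting patients who followed their practitioner's guidance" and went on to install and use the app. The third, Dashboard Use, is "the average number of times each practitioner logs on to the online FOCUS dashboard" to look at their own patients' data. Acceptability and readiness scales follow.
- Under "Providers at the clinic who may not have been directly involved with the FOCUS Intervention" stand contextual scales, with no uptake measure.

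Section 4.1 says staff are chosen purposively and times their first survey by when their own patient starts treatment. It also describes a search of health records by diagnosis: "This procedure generates a list of active patients who meet diagnostic inclusion criteria". Agencies that cannot run the search audit caseloads instead.

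The SAP (Analytic Approach) measures penetration before facilitation starts, at 3 months and at 6 months, and models rates by negative binomial regression with log offsets. It does not say which measures make up penetration or which clinicians are analysed. The Power Analysis expects 20 clinics, 5 clinicians per clinic and 3 patients per clinician.

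**The concern.** Under section 5.1 (Study Sites), clinics are randomised and facilitators then work to engage practitioners. Receiving FOCUS data comes after that, and is something the strategy may change. The background expects internal facilitators to gain penetration through existing relationships and team meetings.

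If penetration is computed only among receivers, the two arms are compared on groups of clinicians that the strategies themselves helped to select. Two things follow. Randomisation no longer protects the comparison. And the number of clinicians each strategy brings in, which is a large part of what penetration within a clinic means, is left out. The Aim 2 mediation and moderation models build on the Aim 1 models, so they would inherit both problems.

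**Working it through.** **1. What each measure needs before it can be computed.**

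| Measure | Needs | Defined for a clinician who never offers FOCUS? |
|---|---|---|
| Offered mHealth | the clinician's eligible patients | yes, it is 0 |
| Treatment Initiation | consenting patients | no, the denominator is empty |
| Dashboard Use | own patients' uploaded data | only as a log-on count with nothing to view |

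Offered mHealth is the only one whose denominator exists before any uptake. It is listed under the same restrictive label as the other two.

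**2. Is the clinician set widened elsewhere?** No passage brings in all clinicians at a clinic or those with no offers. The log-offset model can hold zero counts, but only for clinicians who are in the dataset. The pre-facilitation baseline needs a set of clinicians named before anyone could have received FOCUS data in the trial, so it does not fit the label in section 5.1.

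**3. Planned numbers.** 20 × 5 = 100 clinicians, 100 × 3 = 300 patients and 300/20 = 15 patients per clinic, which agree with each other and with section 5.1. The documents give no assumed penetration or take-up rate. The SAP's provider-level detectable effect (d = 0.55) contains none either, and this point does not depend on it.

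**4. How restriction can change the comparison.** Let *u* be the share of clinicians with eligible patients who take FOCUS up, and *p* the mean offer rate among those who do. With equal caseloads and non-adopters at 0:

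- rate among receivers = *p*
- rate over all clinicians = *u* × *p*
- if p(A) > p(B), the ranking reverses only when u(A)/u(B) < p(B)/p(A)

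All values of *u* and *p* below are assumed, with 50 clinicians per arm for illustration.

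| Arm A | Arm B | Receivers only, A v B | All clinicians, A v B |
|---|---|---|---|
| 10/50 at 80% | 40/50 at 50% | 80% v 50% | 0.20 × 0.80 = 16% v 0.80 × 0.50 = 40% |
| 20/50 at 70% | 40/50 at 50% | 70% v 50% | 0.40 × 0.70 = 28% v 40% |
| 25/50 at 60% | 50/50 at 50% | 60% v 50% | 0.50 × 0.60 = 30% v 50% |
| 25/50 at 80% | 40/50 at 50% | 80% v 50% | 0.50 × 0.80 = 40% v 40% |
| 40/50 at 80% | 40/50 at 50% | 80% v 50% | 0.80 × 0.80 = 64% v 40% |

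With offer rates of 80% and 50% the break-even take-up ratio is 0.50/0.80 = 0.625. The fourth row sits on it (0.50/0.80). In the last row take-up is equal and the ranking stands.

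**The case against.** The strongest reply is that a label in an ethics form is being read as an analysis rule. Section 5.1 states no exclusion and does not use the word penetration. The labels are also loose: the absorptive capacity scale stands under the second one, yet is meant for practitioners engaged in implementation. The label used for the uptake measures could simply mean clinicians set up to receive data. The introduction to the staff survey covers exposure to FOCUS and its adoption, and is not limited to data receivers. All of this stands. A reader might infer that non-adopters are dropped by rule. The documents do not say so; they fail to provide for counting them.

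A reader might also infer that the arms will be ranked the wrong way round. That rests wholly on assumed rates. If exactly 5 clinicians took part at equally sized clinics in both arms, *u* would be the same and no reversal could come from numbers alone. This does not rescue the measure, however. Which five take part can still depend on the strategy, and a fixed five per clinic cannot show breadth at all.

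Nor is penetration declared the main outcome. Aim 1 names it first, beside acceptability, cost and cost-effectiveness.

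A further objection limits the remedy. With 15 patients per clinic at 3 per clinician, 15/3 = 5 clinicians would have a FOCUS patient. At a clinic with, say, 12 clinicians (assumed), 12 − 5 = 7 would have none in either arm. Scoring their log-ons as 0 would partly measure the enrolment target, so zero-scoring should not extend to Dashboard Use.

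Finally, section 4.1 gives the active list to care coordinators or team leaders with a script, so offering is not left only to keen clinicians. That may narrow differences between clinicians, but it does not define who is counted.

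**Conclusion.** The point holds as an undefined clinician set with a real risk of bias. The only text on the matter attaches the uptake measures to providers who receive FOCUS data, and nothing brings in clinicians with eligible patients who never offer it. That those measures make up penetration is an inference, though a sound one: the documents offer no other provider uptake measure. A comparison restricted in this way conditions on something that happens after randomisation and that the strategy can affect. It omits breadth of uptake, and it conflicts with the background description and with the SAP's baseline.

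Neither the size nor the direction of the bias can be derived from the documents. The assumed cases run from no change in ranking to a reversal of 80% v 50% into 16% v 40%. A reversal needs take-up to differ between arms by more than offer rates do, in the opposite direction. The documents give no figure that makes this likely or unlikely.

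**What to change.** - State in the SAP that penetration is based on Offered mHealth, over all clinicians at each clinic with at least one patient on the diagnosis-based active list of protocol section 4.1, with the list fixed at or before randomisation.
- Use each clinician's coded count of listed eligible patients as the log offset, and count clinicians with no offers as 0.
- Add the clinic-level share of these clinicians with at least one offer, so that breadth is reported directly.
- Keep Treatment Initiation and Dashboard Use as secondary measures among clinicians with an enrolled FOCUS patient, labelled as such.
- Reconcile the section 5.1 label with the SAP's pre-facilitation baseline.

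The cost is modest. The lists are already to be made, but each clinic must return coded per-clinician counts, by caseload audit where a diagnosis search is not available. A single total of clinicians per clinic would not be enough, because the model needs an offset for each clinician. Nothing in the documents says that the lists will be kept by clinician, so the counts should be secured when the lists are made. Penetration figures will be lower than among receivers alone.
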